Appendix 10: Appointment Reminder Card

Appendix 11: Completion Certificateions" Leaflet for
Mailing

TCU
1920-347
Approved on 2-8-2023
Expires on 1-24-2024

Summary

The purpose of the Substance Use and Health Risk Intervention (SUHRI) project is to adapt and test an integrated health risk-reduction and motivational enhancement intervention (a cloud-based app) for Juvenile Justice (JJ) youth that will ultimately be (after full testing through a subsequent large-scale RCT) a sustainable intervention implemented within a JJ supervision/case management context to teach and facilitate positive, prosocial, and expected behaviors. The intervention will use interactive graphical approaches to encourage introspection and problem identification, enhance self-regulation, improve analytical problem-solving skills, and promote healthy behaviors in two inter-related target areas: substance use and risky sex practices. App sessions will be self-directed (require minimal instruction/interaction assistance), and also include a service referral piece whereby youth are provided with additional resources for seeking services related to risky health behaviors and substance use.

This research will be carried out in two pilots: (1) Intervention Adaptation and Feasibility and (2) Protocol Feasibility. The specific aims of the project are to (a) examine intervention feasibility and acceptability (Pilot 1), (b) *test the feasibility of the study protocol (adherence, subject retention, instrumentation) with JJ-involved youth (Pilot 2).*

During Pilot 1, intervention content will be adapted from existing evidence-based interventions so that it is developmentally appropriate for the target population and suitable for a web-based format. During Pilot 2, a test of the intervention will yield data on intervention feasibility, acceptability, and impact on youth outcomes. Proximal outcomes include improvements in change mechanisms (e.g., problem recognition, decision making, intention to reduce personal risk) and service initiation (SU or STI-related services). Distal outcomes include reduction in risky behaviors, including substance use (self-report and urinalysis) and sexual health risk (self-reported risky sex practices). Successful completion of the aims will result in an intervention that is appropriate and feasible for use with JJ-involved youth.

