To ensure fidelity to the study protocol and to avoid any perceived coercion by JJ staff, TCU Institute of Behavioral Research (TCU/IBR) RAs will oversee intervention administration, including voluntary study enrollment and withdrawal if requested. Following our NIDA-funded JJ- TRIALS study protocol, NO participant information (youth participation, youth assessment responses, choices/responses selected during the intervention, completion of sessions) will be shared with JJ staff; only aggregate information will be shared with JJ leadership.

11. Location:

All intervention and assessments sessions will take place either online using a platform such as Zoom, in-person at a Tarrant County Juvenile Services office or another public place, or via a tablet hand-off in an agreed upon public place. All TCU rules and regulations regarding COVID-19

protocols will be followed for in-person interactions including masking, hand-washing/sanitizing, social distancing when able, and sanitizing of all equipment.

12. Subject Population:

Participants will include juvenile justice-involved youth on probation within at least 1 local juvenile probation department (Tarrant County, currently). The Tarrant County Board (TCJS) has granted preliminary approval to submit appropriate requests to TJJD to move forward with planning this study.

We expect to recruit approximately 60 youth who range in age from 14 to 18 years old.

Inclusion Criteria: Youth ages 14-18 on community supervision are eligible if they have 1 or more indicator(s) of substance use, are English-speaking, and have no indication of current suicide risk or severe cognitive impairment/thought disorders. Youth's parent/legal guardian may be Spanish-speaking. Upon approval of the parental consent document, it will be translated into Spanish and submitted to the IRB for approval.

Exclusion criteria: Youth who are on TJJD (state) supervision rather than county supervision are not eligible to participate. In addition, youth who are currently suicidal, homicidal, or otherwise severely impaired (e.g., active psychotic symptoms) such as severe cognitive impairment or thought disorders are not eligible. Youth younger than 14 and youth 19 or older are likewise not eligible.

13. Recruitment Procedure:

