Implementation feasibility measures will be recorded, summarized, and reviewed monthly by the PI and team in order to inform real-time protocol adjustments (e.g., changes in recruiting practices if target numbers are not reached). Once the targeted youth recruitment goal has been achieved, psychometric properties of baseline measures will be conducted (means, SD, coefficient alpha, exploratory/confirmatory factor analysis). Because the design calls for repeated measures at baseline, month 1, and month 3, measures will not be revised between administration points.

However, psychometrics (conducted on data from all time points) will be used to inform modifications prior to a full-scale R01 RCT and reliability of scales for use in exploratory analyses of intervention efficacy.

Baseline characteristics will be included as covariates in analyses. The distal outcome will be the percent of study subjects who use drugs (self-report, corroborated with positive urine test) at follow-up (1- and 3-months). All study participants (regardless of study retention) will be included in analyses (i.e., an intent-to-treat approach; ITT). Baseline variables that directly relate to our aims (e.g., drug use, risky sex practices) will be evaluated for use as covariates. Abstinence at each

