follow-up time point will be compared using chi square test. Our proximal outcomes will include putative measures (e.g., problem recognition, decision making, intention to reduce personal risk) and receipt of SU services (dichotomous measure from youth records). Because proportions of females and their SU rates are generally lower among JJ youth compared to males,⁶ and males/females may respond differently to MEC interventions,¹⁶ we will explore sex (as a biological variable) differences in SU, risky sex practices, and exploratory outcomes using univariate analyses (e.g., chi square, t-tests, ANOVA). We will also explore potential racial/ethnic disparities in order to more fully inform whether cultural modifications are needed for a subsequent application. A log rank test will be used to assess intervention dropout. Participants who withdraw consent or are lost to follow up will be missing on outcome measures. To address this, stochastic multiple-imputation will be attempted, which will provide maximum likelihood estimates, account for uncertainty in missing values, and provide unbiased estimates of the treatment effect if data are missing at random. Effect sizes will be used to calculate sample sizes needed for the larger R01. Calculations will include samples needed to assess intervention feasibility across sex and race/ethnicity subgroups.

21. Check List for the Items That Need to be Submitted:

a. Protocol	
b. Consent document	
c. HIPAA form if applicable	
d. Protecting Human Research Participants Training certificate for each investigator	
e. Recruitment flyers, letters, ads, etc.	
f. Questionnaires or other documents utilized in screening and data collection	

Principal Investigator Assurance

22. By signing below, I certify to the following:

- The project described herein will be conducted in accordance with applicable TCU policies and procedures, as determined by the IRB of record. All Human Subject Research projects occurring at TCU must be conducted in compliance with the Office of Human Protection ("OHRP") regulations at 45 CFR 46 and all other applicable federal and state laws and regulations (collectively "Applicable Law")
- I have a working knowledge of Applicable Law

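### Section 20 analyses drug use only as any use versus none, so a youth who cuts down without quitting counts as unchanged and the drug-use effect size carried to the R01 cannot show partial reduction

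*Combined protocol and SAP*

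**What the plan says.** The Summary of the combined protocol and SAP states the target as a reduction: "Distal outcomes include reduction in risky behaviors, including substance use (self-report and urinalysis". It gives no measurement scale. The specific aim of Pilot 2 is to "test the feasibility of the study protocol (adherence, subject retention, instrumentation) with JJ-involved youth".

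Section 20 (Data Analyses) fixes the scale: "The distal outcome will be the percent of study subjects who use drugs", by self-report corroborated with a urine test, at 1 and 3 months. Abstinence at each "follow-up time point will be compared using chi square test". Baseline drug use has a supporting role only: "Baseline variables that directly relate to our aims (e.g., drug use, risky sex practices) will be evaluated for use as covariates". The section ends by carrying results forward: "Effect sizes will be used to calculate sample sizes needed for the larger R01".

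Section 12 sets the size and the population: "We expect to recruit approximately 60 youth who range in age from 14 to 18 years old", with youth "eligible if they have 1 or more indicator(s) of substance use". No alpha, power, expected use rate or target effect is given.

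**The concern.** The intervention is described as risk reduction, it consists of four app sessions, and entry requires some sign of substance use. Using less without stopping is a plausible response in these youth. A youth who goes from 20 days of use a month to 5 has the same value on the planned outcome as one who stays at 20. No reason is given for reducing self-report to yes/no.

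What is at stake is mainly the next trial. If youth cut down and few quit, the pilot's drug-use estimate will sit near zero. An R01 sample size based on that estimate would be planned without knowledge of the change that occurred.

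**Working it through.** **1. What the plan analyses.** There is no stated power or sample-size figure to reproduce, so the first check is textual.

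- Distal outcome: percent using drugs, or abstinence. Binary.
- Baseline drug use: a candidate covariate. A plain chi-square uses no covariate.
- t-tests and ANOVA: examples for exploring sex differences in substance use, not for testing change in use.
- Proximal outcomes: problem recognition, decision making, intention, and receipt of services. None measures amount used.

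No named analysis estimates change in how much a youth uses.

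**2. Within-youth illustration.** All inputs except n = 60 are assumptions:

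- days used in the past 30, with a point mass at zero;
- gamma-shaped days among users (shape 1), mean 10 at baseline;
- latent correlation of 0.6 between baseline and follow-up;
- two-sided 5%, 1,000 simulated trials per scenario.

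McNemar's test on any use is compared with the Wilcoxon signed-rank test on change in days. Power is shown as any use v days:

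| Effect | 50% using at baseline | 70% | 90% |
|---|---|---|---|
| Mostly cutting down (days −30%, users −10% relative), n = 60 | 11% v 43% | 17% v 66% | 41% v 90% |
| Same effect, n = 48 (80% of 60 followed) | 9% v 34% | 14% v 58% | 31% v 79% |
| Cutting down, none quit, n = 60 | 5–6% v 23% | 5–6% v 41% | 5–6% v 66% |
| Mixed (days −20%, users −20%), n = 60 | 27% v 46% | 48% v 70% | 88% v 90% |
| Quitting only, n = 60 | 28% v 19% | 53% v 32% | 86% v 47% |

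Repeat runs of the first row gave 10–12% v 38–43%, 16–17% v 66–67% and 35–41% v 89–90%. The mixed effect at 90% use came out level in repeat runs (88% v 88%, 89% v 89%). The figures are therefore approximate. Type I error was about 3% to 7% for both tests.

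Relative loss from the binary scale under the mixed effect: 1 − 27/46 = 41%, 1 − 48/70 = 31%, 1 − 88/90 = 2%.

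**3. Two-group illustration.** This uses a different model, to see whether the direction depends on the first. Assume 30 v 30, two-sided 5%, and a normal latent amount of use shifted by d = 0.5 SD. The cut point is c = Φ⁻¹(p), where p is abstinence in the comparator.

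- Power on amount: Φ(d√(30/2) − 1.96) = Φ(0.5 × 3.873 − 1.96) = Φ(−0.024) = 49%.
- Power on abstinence, p against Φ(c + d), pooled-variance test of two proportions: 18%, 23%, 30%, 32% and 32% at p = 5%, 10%, 20%, 30% and 50%.
- Share of information kept, φ(c)²/[p(1 − p)]: at p = 5%, 0.1031²/0.0475 = 22%; at p = 50%, 0.3989²/0.25 = 64%.
- Number per arm for 80% power: 63 on amount; 217, 152, 115, 103 and 102 on abstinence at the same values of p.

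A two-group simulation of days used (log-transformed t-test against chi-square) had 10%, 30% and 50% abstinent in the comparator. When users halved their use and none quit, power on days was 51%, 26% and 13%, against about 5% on abstinence. When the only effect was 20 points more abstinence, the binary test won: 48% v 30%, 35% v 29% and 33% v 27%.

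Both models agree. Frequency is better when youth cut down, and abstinence is better when they quit outright.

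**The case against.** The strongest reply has five parts.

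- **Feasibility is the aim.** Pilot 2 makes no power claim, and efficacy analyses are exploratory. This stands, and it limits the severity: at 30 v 30, even amount of use has only 49% power at d = 0.5. It does not remove the point, because Section 20 says effect sizes will feed the R01.
- **A fall in the percent using is itself a reduction.** This also stands. A reader might infer that the Summary and Section 20 contradict each other, but the Summary states no scale and promises no frequency outcome. The gap is that Section 20 captures only one form of reduction.
- **Any use is the only corroborated measure.** Urine tests support it, and self-reported frequency among youth on probation has no such check. This is a good reason not to replace the outcome, but it is no reason against adding a second.
- **Amount may enter elsewhere.** The sex comparisons allow t-tests and ANOVA, and baseline drug use may be recorded on a fuller scale. It would be too strong to say that amount appears nowhere. Still, nothing prespecifies an analysis of change in amount.
- **The R01 may draw on other outcomes.** Section 20 speaks of effect sizes in the plural, and nothing says the R01 will be sized on abstinence alone. The supported claim is narrower: the drug-use effect, as now defined, cannot include partial reduction.

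A reader might also infer that most of the power to see a reduction is lost. The documents contain no rates from which that could be derived, and the illustrations show it only when cutting down dominates or abstinence is rare.

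**Conclusion.** The point holds in a limited form. From the text alone, drug use is analysed as any use or abstinence, so a youth who uses less but still uses counts as unchanged, and the drug-use effect size for the R01 cannot register that change.

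The size is conditional. Under the assumptions shown, at n = 60, the frequency scale has clearly more power when cutting down dominates (about 11–41% v 38–90%). It has about the same power for a mixed effect at 90% baseline use, and less when the effect is quitting alone (53% v 32% in favour of any use, at 70% using). Neither scale is best throughout.

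The power figures do not describe the planned chi-square or the model proposed below. McNemar and Wilcoxon stand in for them. What the chi-square compares is itself unclear: Section 15 gives every youth the intervention, while the safety monitoring text mentions a comparison group. The pre/post and 30 v 30 set-ups are both assumptions. Confidence is high in the textual point and low in any particular percentage. This is a cheap improvement, not a flaw that invalidates the pilot.

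**What to change.** In Section 20, keep the percent using drugs (self-report corroborated by urine test) as the distal outcome, and add:

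> Where the battery records frequency, change from baseline in self-reported frequency of drug use at months 1 and 3 will also be analysed, using the full item scale and a model that accounts for baseline use and repeated measures, and reported as an estimate with a 95% confidence interval. Effect sizes on both scales will be reported for R01 planning.

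The cost is a short text change and one extra model on assessments already scheduled at baseline, month 1 and month 3, with no new visits or youth. This depends on the battery, which is not in the supplied text, recording frequency. Items that record only yes/no keep the present analysis. The downside is that urine tests cannot corroborate frequency, so the added result should be labelled as resting on self-report and read beside the binary one.

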Following assent and assessment the youth will receive a tablet to use during the study. The RA will walk through a tutorial with youth to ensure they learn how to use the tablet. The youth will then have the first intervention session with the RA. The RA will complete administrative procedures to ensure the youth is presented with the correct modules for the session, and the youth will complete the session independently with the RA available to answer questions. Once the youth completes the session, they will complete an end of session evaluation (using Qualtrics), and the RA will transition the youth out of the session and schedule the next session or the follow-up assessment (following the 4th session of the intervention).

The first intervention session will occur approximately a week after the consent/assent meeting, and each session will occur a week to several weeks apart (spanning across approximately 1 month).

Following the last session, the youth will be scheduled to complete a 1-month assessment either in-person or online with the RA. The youth will receive 2 reminder e-mails and text messages leading up to the assessment appointment. The youth will also complete a 3- month post- intervention assessment proctored virtually or in-person by the RA. The youth will also receive 3 reminder e-mails and text messages leading up to the final assessment. Reminder e-mails will come from the e-mail address [contact] with the subject line "SUHRI Reminder" directly to the youth's personal e-mail address to reduce the chance that another individual will see the e-mails. No reference to a research project will be made in the text.

Each follow-up assessment will last approximately 60 minutes, with intervention sessions lasting approximately 60 – 90 minutes each.

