To request corroborating data from the local JJ department as well as the Texas Department of Juvenile Justice (TJJD), the research team will request that the TCJS research director provide the TJJD-based identification number (PID) for consenting participants as well as demographic, substance screening and assessment, and relevant service attendance information. These data will be shared via a spreadsheet available to the director of research and the research team via Box.com – a secure file-sharing platform. The research team will provide the PID numbers along with headquarters county ID to the TJJD data team via spreadsheet in a Box folder in return for state-level data specific to the youth's substance use screening and assessments as well as offense, background, and service-seeking data. The TJJD research proposal submitted in September 2020 can be found in Appendix 9. be found in Appendix 9.

Intervention

The youth will receive 4 sessions of the interactive, cloud-based intervention administered via a tablet we give them. Each session of the intervention will focus on one of topics associated with drug use and risky sex practices. The final session will include an integrated module ensuring that youth process through a scenario that examines how drug use and risky sex behaviors are related. The youth will complete the final WORK-IT scenario within the app with processing questions (see Appendix 5.7) to work through this integrated scenario and also a quiz-like activity on Kahoot to learn more about local resources for substance use and sexual health.

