Each session includes two modules including a WORK-IT module where youth will work through a scenario they select using the WORK-IT framework. The other module includes two interactive games; the Escaping the Downward Spiral (EDS) game and Jeopardy style trivia. In the EDS game, youth will play a game that focuses on decision-making in scenarios involving substance use and sex, while in the Jeopardy style game, they will learn about facts around substance use and risky sexual decision-making. Participants may receive a small token (e.g., fidget spinner or equivalent toy of size/cost) if they answer a certain number of questions correctly in the trivia game at the end of the intervention sessions. If the last session is virtual, RAs will offer to mail the token to participants and request their mailing address to do so. The tokens will be mailed with a "congratulations" leaflet (Appendix 12) that congratulates the participant on winning the trivia and requests them to be on the lookout for a follow-up survey (the assessment session). Intervention sessions will last approximately 60 - 90 minutes. The youth will complete these independently on a tablet/computer but the RA will be available in-person or via virtual platform to proctor participation. Modules also include the provision of additional information and service information related to substance use and risky sex practices.

Assessment

Participants will be asked to complete a battery of assessments at baseline, 1-month post-baseline, and 3 months post baseline. The assessment/measures package has been approved in several submissions across the initial study submission, AM 1, AM 2, AM 4, and AM6. Participants will also be asked to complete post-session feedback for each intervention session (approved on AM 2 & AM4).

Compensation / Community Service Hours

Compensation will be provided to the youth either in form as a gift card or community service

credits for each intervention session. Youth will get to decide at each session if they want to receive a gift card or community service credit. They can receive \$20 or 3 community service credits for each intervention session. They will also receive \$20 for each follow-up assessment session. Youth will also be reminded at each session that the project activities will end on August and they will be compensated for the activities completed before then.

16. Potential Risks and Precautions to Reduce Risk:

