I Lightning	V Platinum	September → Horn
J Silver	W Iron	October → Scale
K Gold	X Emerald	November → Claw
L Magic	Y Bright	December → Tail
M Venom	Z Stone	

The research design requires that client subjects be linked across assessment completion and to agency records. All participants will be assigned an arbitrary research ID that will be used to link all of their data. Data forms will only be identified with the research ID, personally identifying information will not appear on data forms. The PI will keep a link file linking names and research IDs on a secure server that does not contain other data. The assessments are intended to be administered online using Qualtrics. The RA will prepare the online assessment, which the participant will access by using a personalized link that is connected with their unique participant ID.

In order to personalize the virtual intervention and app experience, at the beginning of the first session, the RA will log the youth into the system using the client research id, the client will be asked to create their own unique user name, called a “FROG NAME.” Similar to the games on social media that provide users with a formula for creating fantasy names (see image to right), the youth will be presented with a formula to create their Horned FrogName.

For example:

First letter of your first name: R=Tangerine Month you were born: April=Canvas Favorite color: Black=17 Your FROG NAME is: TangerineCanvas17

On subsequent intervention sessions, the youth, once logged in by the RA, will be greeted with their unique frog name (e.g., “Hello TangerineCanvas17!”) while completing the virtual intervention session.

TCU computers are secured by redundant firewall and password access (to both the network domain and email user accounts). Procedures for confidentiality will include de-identified data to assure confidentiality. The general policy adopted by the present investigators is based on those used successfully for many years in other similar projects. Research files at the TCU Institute of Behavioral Research (IBR) do not include the names of the subjects involved in studies. In accordance with standard procedures used by the IBR, the confidentiality and privacy of client information will be protected by well-planned and comprehensive procedures. Only unique code numbers assigned by program staff during

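### Does the urine-corroborated drug-use outcome need a written scoring rule for absent or discordant tests?

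*Combined protocol and SAP*

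**What the plan says.** Section 20 (Data Analyses) sets the distal outcome as "the percent of study subjects who use drugs (self-report, corroborated with positive urine test) at follow-up (1- and 3-months". It compares abstinence at each follow-up by chi-square and does not define abstinence separately. The Summary pairs self-report with urinalysis, without saying how they combine. Nothing else in the body of the plan deals with urine testing.

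Section 15 (Study Procedures) describes the outside data, in a paragraph that opens "To request corroborating data from the local JJ department as well as the Texas Department of Juvenile Justice (TJJD". The state request covers "substance use screening and assessments as well as offense, background, and service-seeking data". The county request covers demographics, substance screening and assessment, and service attendance. The reader is sent to Appendix 9 for the state proposal.

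Follow-up visits may be virtual or in person, and Section 19 says "The assessments are intended to be administered online using Qualtrics". No specimen step is described.

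Section 20 names a source for one proximal outcome, "receipt of SU services (dichotomous measure from youth records", but none for urine. On missing data it says "Participants who withdraw consent or are lost to follow up will be missing on outcome measures" and proposes multiple imputation.

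On timing, Section 15 says under Procedures "The youth will also complete a 3- month post- intervention assessment proctored virtually or in-person by the RA", but under Assessment "a battery of assessments at baseline, 1-month post-baseline, and 3 months post baseline".

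**The concern.** A composite of self-report and a laboratory test needs a rule for every combination of the two, and Section 20 gives none. Three cases are open: reported use with no test, reported use with a negative test, and denied use with a positive test. The missing-data sentence names youth who withdraw or are lost, so it does not plainly cover a youth who completes the visit but has no urine result.

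Suppose a positive test were required and an absent test scored as non-use. Recorded use would then fall in proportion to how often the agency tests. Differences in testing between visits, or between sex or racial/ethnic groups, could pass for differences in use. If untested youth were set to missing, the usable sample would shrink to those tested. Section 20 plans such subgroup comparisons and means to size a later trial from the effect sizes. A rule chosen after the data are seen could move those numbers.

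**Working it through.** The plan states no expected use rate, test coverage, power or significance level, so there is no figure of its own to reproduce. The only input from the documents is the planned sample of about 60 (Section 12). Everything else here is assumed.

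**Inputs.** True use p = 0.50; self-report sensitivity S = 0.8; urine sensitivity U = 0.7; fraction tested c = 1, 0.5 or 0.25; independent errors; perfect specificity.

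**Formulas.**
- Positive test required, absent test scored as non-use: p·S·U·c
- Self-report alone: p·S
- Either source positive: p·[1 − (1 − S)(1 − c·U)]

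| Coverage | Test required, absent = non-use | Self-report alone | Either source |
|---|---|---|---|
| 1 | 0.5×0.8×0.7×1 = 28% | 0.5×0.8 = 40% | 0.5×(1 − 0.2×0.3) = 47% |
| 0.5 | 14% | 40% | 0.5×(1 − 0.2×0.65) = 43.5% |
| 0.25 | 7% | 40% | 0.5×(1 − 0.2×0.825) = 41.75% |

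Of 60 youth, the first column is about 17, 8 and 4, and self-report is 24. If untested youth are instead missing, the test-required rate is 28% at any coverage, but n is 60, 30 or 15, with 95% Wilson intervals of 18–40%, 15–46% and 12–53%.

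**Where the spread comes from.** Either source minus self-report is p·(1 − S)·c·U. In the table this is 7, 3.5 or 1.75 points. Over a wider assumed grid (p 0.4–0.6, S 0.6–0.8, U 0.5–0.8, c 0.25–1) it runs from 0.4×0.2×0.25×0.5 = 1 point to 0.6×0.4×1×0.8 = 19.2 points. The top of that range needs every youth tested, in which case both rates can be reported on the full sample. For scale, the 95% half-width of one proportion near 50% with n = 60 is 1.96×√(0.25/60) = 12.7 points. The large gaps in the table come from the first column.

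**Does the plan adopt that first rule?** Three things in the text count against it.
1. In Section 20 self-report is the measure and the urine test is said to corroborate it. The Summary also puts self-report first.
2. Nothing says an absent test is a negative test. Section 20 keeps all participants in the analysis and imputes missing outcomes, so scoring an absent test as non-use would depart from that approach.
3. The sentence on withdrawn and lost youth says they will be missing. It does not say that only they will be.

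**Is the urine source really absent?** Section 15 calls the agency data corroborating and includes substance screening, which could hold urine results. Appendix 9 and the measures package mentioned in Section 15 are not reproduced, so neither a urine field nor a specimen step can be ruled out.

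**The case for a change.** The strongest reply is that no sentence in Section 20 excludes the damaging rule. Corroborated with a positive test can be read as confirmed by one. Even if agency records do hold dated urine results, the scoring of discordant pairs and the date window are still unwritten. Testing the instruments is a stated aim of this pilot, so test coverage and agreement with self-report would be useful results, and writing the rule would cost only a few sentences.

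All of that is true as far as it goes: the rule is unwritten. But the obvious repair is not clearly better. Making either source the primary definition keeps the dependence on agency testing that prompted the worry: 41.75% to 47% as coverage rises from a quarter to full. With specificity 0.95 for both sources it gives 44.8% to 51.9%, above the assumed true 50% at full coverage. Self-report alone does not move with coverage (40%, or 42.5% with specificity 0.95), but it misses youth who deny use. Choosing between them is a judgement on which statisticians differ.

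The two anchors for the 3-month visit do conflict and must be reconciled. That is a separate scheduling matter and does not show the outcome definition to be defective.

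**Conclusion.** No change to the plan follows. The gap is real but of a kind that analysts fill sensibly: score use from self-report, show urine results beside it with the number tested and the agreement, and leave an absent test as absent. The alarming figures (28%, 14% and 7% against 40%) depend on a rule the plan does not state and on assumed prevalence, sensitivities and coverage. They show that scoring rules can differ; they do not show that this study's result would be distorted.

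Between the two ordinary readings the difference is 1.75 to 7 points under the base assumptions and 1 to 19.2 points over the wider grid. The study's stated aim is protocol feasibility, Section 20 calls its efficacy analyses exploratory, and no power calculation or decision threshold rests on this outcome. Its use in sizing a later trial is already limited by a half-width of about 13 points.

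The conclusion rests on reading self-report as the measure and urine as support, and on the unseen appendix and measures package not contradicting that. If they showed that a positive test was required and absent tests were counted as abstinent, the concern would need to be reopened.
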